## 13.0 Pooled Analyses Across Cohorts

The analyses specified in Sections 12 will be performed separately for each cohort, where applicable. In addition, the following summaries and analyses may be performed on the pooled cohorts for exploratory purposes. If performed, summaries and analyses will be presented by dose level (60 mg SPX-101 Cohort 1, 120 mg SPX-101 Cohort 1 and 2, and pooled placebo) and overall.

- Summary of subject disposition
- Summary of subject demographics
- Summary of CF history
- An ANCOVA as described in Section 12.6.1, using baseline ppFEV1 use as a covariate.

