### 7.3.2 Rationale for Cohort 2 Dosage

In Cohort 1, a total of 45 adult subjects with cystic fibrosis were treated with one of two doses of SPX-101 (60 mg BID and 120 mg BID) or matching placebo, and 40 subjects completed the study.

The SPX-101 120 mg BID group demonstrated an improvement in the primary endpoint, trough ppFEV1 at day 28, (least squares mean difference from placebo  $\pm$  standard error) of  $3.08 \pm 2.411$ ;  $p = 0.21$  for the SPX-101 60 mg BID group and  $5.19 \pm 2.606$ ;  $p = 0.05$  for the SPX-101 120 mg BID group (source: Table 14.2.1.1).

SPX-101 was well tolerated in both dose groups with no dose-limiting toxicity observed. There were no deaths in the study. Two subjects had serious adverse events (SAEs); one subject had tachycardia and one subject had cough and dyspnea, and both subjects were in the SPX-101 120 mg BID group. Treatment-emergent adverse events (TEAEs) were reported for 71.4%, 66.7%, and 75.0% of subjects in the placebo, SPX-101 60 mg BID, and SPX-101 120 mg BID treatment groups, respectively. TEAEs that coded to the Medical Dictionary for Regulatory Activities (MedDRA) System Organ Class of Respiratory, Thoracic, and

Mediastinal Disorders were reported for 35.7%, 53.3%, and 43.8% of subjects in the placebo, SPX-101 60 mg BID, and SPX-101 120 mg BID treatment groups, respectively. Although more respiratory TEAEs were reported for subjects on active treatment than placebo, the most commonly reported respiratory TEAEs were associated with the therapeutic effect of SPX-101: sputum increased was reported for 7.1%, 20%, and 12.5% of subjects in the placebo, SPX-101 60 mg BID, and SPX-101 120 mg BID treatment groups, respectively; and cough was reported for 0%, 26.7%, and 6.3% of subjects in the placebo, SPX-101 60 mg BID and SPX-101 120 mg BID treatment groups, respectively. The only pre-defined adverse event of special interest was hyperkalemia, which was not reported for subjects in any treatment group. [Table 1](#) shows these results.

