### 9.4.1 Inclusion Criteria

Subjects must satisfy all of the following inclusion criteria before they will be allowed to participate in the study:

1. Ability to provide written, personally signed, and dated informed consent to participate in the study, in accordance with the ICH GCP Guideline E6 and applicable regulations, before completing any study-related procedures
2. Ability and willingness (in the judgment of the Investigator) to attend study visits and fully comply with study procedures and restrictions; each subject's study visits will occur at approximately the same time of day throughout the study and under specified conditions with respect to daily respiratory clearance and medication regimens
3. Ability to self-administer the investigational product
4. Male or nonpregnant, nonlactating female subjects aged 18 to 50 years inclusive

5. Diagnosis of cystic fibrosis as determined by the 2008 Cystic Fibrosis Foundation Consensus Guidelines for Diagnosis [1], defined as the presence of clinical signs and symptoms of CF in conjunction with at least 1 of the following:
  - a. Documented sweat chloride test result  $\geq 60$  mEq/L by quantitative pilocarpine iontophoresis
  - b. Two well-characterized, disease-causing genetic mutations in the CFTR gene; the original documentation of genetic testing is not required if the specific mutations are documented in the subject's medical record.
6. ppFEV1 as follows:
  - a. Cohort 1: between 40.0% and 80.0%
  - b. Cohort 2: between 50.0% and 80.0%

Note: spirometry must be performed in accordance with American Thoracic Society (ATS)/European Respiratory Society (ERS) end-of-test criteria and the Global Lung Initiative (GLI) predicted values [2; 3]
7. Stable CF lung disease, defined as no pulmonary exacerbation or acute upper or lower respiratory illness other than CF within 28 days preceding screening, except for allergic or nonallergic rhinitis; in addition, subject must not have had any of the following:
  - a. Significant hemoptysis (at the discretion of the Investigator) within 28 days of screening
  - b. Pneumothorax within 28 days of screening
  - c. Diagnosis of active allergic bronchopulmonary aspergillosis (at the discretion of the Investigator)

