## 6.2 Randomization

The Investigator or designee will use an Interactive Voice/Web Response System to randomize eligible subjects for each cohort. In Cohort 1, randomization was stratified by the Visit 2 pre-dose ppFEV1 (between 40.0% and 55.0% vs between 55.1% and 80.0%). Only those subjects who met the randomization criteria were eligible for assignment to study treatment. Subjects who failed to meet the randomization criteria could have had Visit 2 repeated once, or they were considered screen failures. In Cohort 2, randomization was stratified by concomitant use of hypertonic saline. NOTE: The Cohort 2 FEV1 entrance criterion was modified to require a screening ppFEV1 between 50 – 80% of predicted normal thus no stratification by baseline ppFEV1 was undertaken.

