### 12.6.1 Primary Variable

#### Primary Efficacy Analysis

The primary efficacy endpoint is the change from baseline in ppFEV1 at visit 5 (week 4). The change from baseline in ppFEV1 at each visit (Weeks 1, 2, and 4) will be summarized and compared between each treatment group and placebo. No imputation of missing data will be done for this analysis.

The comparison between each treatment group and placebo will be evaluated by using an analysis of covariance (ANCOVA) model, which will include treatment as the factor, and the stratification factor as a covariate (i.e., baseline lung function categories [ppFEV1 40.0% to 55.0% or 55.1% to 80.0% for Cohort 1] and the concomitant use of hypertonic saline for Cohort 2). Also included in the ANCOVA model for Cohort 2 is baseline ppFEV1. Descriptive statistics will include the number of observations, unadjusted mean, standard deviation, median, first quartile, third quartile, minimum and maximum, and least squares mean. Treatment differences from placebo will be presented and estimated by least squares means from the analysis model along with 95% confidence intervals and associated 2-sided p-values, which are presented for descriptive purposes.

Sponsor: SPYRYX Biosciences

Protocol no: SPX-101-CF-201

---

As described in the power and sample size calculations in Section 6.1, Cohort 1 will be evaluated for success using a two-sided 0.15 significance level. Cohort 2 will be evaluated for success using a one-sided (upper) 0.10 significance level. For Cohort 2, both the one-sided p-value and the lower bound (i.e. one-sided 90% confidence interval) will be presented.

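### The optional pooled ANCOVA in SAP 13.0 has no cohort term, so 60 mg versus pooled placebo is partly a comparison between cohorts

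*SAP*

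**What the plan says.** The main plan analyses each cohort separately (SAP Sections 6.0 and 12.0). Section 13.0 then adds that "the following summaries and analyses may be performed on the pooled cohorts for exploratory purposes". Results would be shown by dose level: "60 mg SPX-101 Cohort 1, 120 mg SPX-101 Cohort 1 and 2, and pooled placebo". The efficacy model is given in one line: "An ANCOVA as described in Section 12.6.1, using baseline ppFEV 1 use as a covariate".

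The section it refers to, SAP 12.6.1, sets out an ANCOVA "which will include treatment as the factor, and the stratification factor as a covariate". That factor is the baseline lung function category in Cohort 1 and hypertonic saline use in Cohort 2. The Cohort 2 model also carries baseline ppFEV1. Neither section mentions a term for cohort.

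The cohorts were run one after the other and differ in several ways:

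- **Arms and allocation:** placebo, 60 mg and 120 mg at 1:1:1 in Cohort 1; 120 mg and placebo at 2:1 in Cohort 2 (SAP 6.0; Protocol Table 4).
- **Entry range for ppFEV1:** 40 to 80% in Cohort 1, 50 to 80% in Cohort 2 (Protocol 9.4.1).
- **Stratification:** by ppFEV1 in Cohort 1, whereas "In Cohort 2, randomization was stratified by concomitant use of hypertonic saline" (SAP 6.2), with about half of Cohort 2 meant to be saline users (Protocol 9.5.9).

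**The concern.** There are two problems.

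First, the model is not fully defined. Section 12.6.1 holds two models with different covariates, so referring back to it does not fix a pooled one. The stray word after baseline ppFEV1 would fit hypertonic saline and does not fit a lung function value, so a reader cannot tell whether saline use was meant to be in the model. Two programmers could fit different models and both claim to follow the text.

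Second, on the plainest reading (treatment plus baseline ppFEV1) the model ignores the cohort within which each subject was randomised. All 60 mg subjects come from Cohort 1, but about half of their placebo comparators come from Cohort 2. Any cohort difference in mean change that baseline ppFEV1 does not explain, for example from calendar period or the mix of saline users, enters the 60 mg estimate as if it were a drug effect. That estimate would be displayed beside 120 mg, which invites a dose comparison.

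**Working it through.** **Inputs**

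- Cohort 1 treated subjects by arm: Protocol 7.3.2 reports adverse event rates of "71.4%, 66.7%, and 75.0% of subjects in the placebo, SPX-101 60 mg BID, and SPX-101 120 mg BID treatment groups". These are 10/14, 10/15 and 12/16. Together with the other percentages in Protocol Table 1, 14, 15 and 16 are the only arm sizes between 10 and 20 that fit. They add to the 45 treated subjects reported.
- Cohort 2 as planned (SAP 6.1): 45 subjects at 2:1, so 15 on placebo and 30 on 120 mg; SD 7.58.
- d: Cohort 1 minus Cohort 2 mean change after baseline adjustment. The documents give no value, so 0 to 4 points is an assumption.

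**The plan's own figure.** The SAP states no figure for the pooled analysis. Its Cohort 2 power (88% to 97% for 6 to 8 points, one-sided alpha 0.10) is reproduced by a noncentral t calculation with 15 v 30 and SD 7.58: 88.4% and 97.8%. The inputs are therefore read as the plan intends.

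**Bias without a cohort term**

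Share of each pooled group from Cohort 1: 60 mg 15/15 = 100%; placebo 14/29 = 48%; 120 mg 16/46 = 35%.

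- 60 mg v placebo: 1 - 14/29 = +0.517 per unit of d
- 120 mg v placebo: 16/46 - 14/29 = -0.135 per unit of d
- 120 mg v 60 mg (not a planned test): 16/46 - 1 = -0.652 per unit of d

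| Assumed d | Bias, 60 mg v placebo | Type I error, 60 mg (two-sided 0.05) | Bias, 120 mg v placebo |
|---|---|---|---|
| 0 | 0 | 5.0% | 0 |
| 1 | 0.52 | 5.5% | -0.13 |
| 2 | 1.03 | 7.1% | -0.27 |
| 3 | 1.55 | 9.8% | -0.40 |
| 4 | 2.07 | 13.6% | -0.54 |

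The type I error column uses SD 7.58 and all 90 subjects. The Cohort 1 estimate for 60 mg is 3.08 (Protocol 7.3.2).

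**Missing Week 4 values.** Of the 45 treated in Cohort 1, "and 40 subjects completed the study"; the arms of the other five are not given. If those five have no Week 4 value, the extremes are:

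- 60 mg v placebo: 0.517 if none is on placebo, 1 - 9/24 = 0.625 if all five are.
- 120 mg v placebo: 11/41 - 14/29 = -0.214 if all five are on 120 mg, 16/46 - 9/24 = -0.027 if all are on placebo.

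**Precision with and without the term** (SD 7.58, baseline covariate left out)

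Without cohort:

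- 60 mg: 7.58 × √(1/15 + 1/29) = 2.41
- 120 mg: 7.58 × √(1/46 + 1/29) = 1.80

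With an additive cohort factor, d is estimated from the two groups present in both cohorts, with information 14×15/29 + 16×30/46 = 7.24 + 10.43 = 17.68:

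- 60 mg: √(2.411² + 0.517² × 7.58²/17.68) = 2.58
- 120 mg: 7.58/√(14×16/30 + 15×30/45) = 1.81

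Both bias multipliers become zero. For comparison, Cohort 1 alone gives 7.58 × √(1/14 + 1/15) = 2.82 for 60 mg. The pooled value of 2.411 matches the 60 mg standard error reported in Protocol 7.3.2 only by coincidence.

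**Break-even.** The cohort term lowers the mean squared error for 60 mg v placebo once 0.517d exceeds √(2.585² - 2.411²) = 0.93, that is, d above about 1.8 points.

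**The case against.** Little rests on this analysis. It is optional and exploratory, success is judged within each cohort (SAP 12.6.1), and a 60 mg estimate against concurrent placebo already exists from Cohort 1. The display labels the 60 mg group as Cohort 1, so the imbalance is visible. All of this stands and sets the weight of the point.

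It can also be said that the line has a natural reading, treatment plus baseline ppFEV1, so the model is not undefined. That is the reading used for the bias figures. Another reading keeps the stratification factors as strata nested within cohort. It would absorb cohort and remove the bias, but the SAP does not say this. That the answer depends on which reading is taken is itself a reason to write the model out. The table shells are in a separate document (SAP Appendix 2) and may settle it; this cannot be checked.

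The size is hypothetical. Visits and endpoint are the same in both cohorts, and the baseline covariate may take up part of the difference in entry range. A residual d near 4 would be more than half the planning SD. This is fair, and is why the range starts at zero.

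The strongest objection is that the cohort term brings its own assumption. With it, the 60 mg contrast puts weights of -0.305 and +0.305 on the Cohort 1 and Cohort 2 120 mg arms. If the 120 mg effect differs by x between cohorts, 60 mg v placebo is biased by 0.305x, which the model without the term avoids. As an illustration, Cohort 1 gave 5.19 for 120 mg and Cohort 2 was planned on 6 to 8, so x might be 0.8 to 2.8. That adds 0.24 to 0.85 points and moves the break-even d to about 1.9 to 2.4. The assumption must therefore be stated, but it does not justify leaving cohort out.

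**Conclusion.** The concern holds and is minor. As written, the pooled ANCOVA has no cohort term and no clear covariate list. On its plainest reading, 60 mg v pooled placebo carries about 0.52 of any residual cohort difference (0.52 to 0.63 allowing for the Cohort 1 non-completers). For 120 mg v placebo the multiplier is small, between -0.03 and -0.21.

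The missing term and the multipliers are well established. They rest on arm sizes derived from reported percentages and on planned Cohort 2 numbers. How large the bias would actually be is unknown, because it depends on d. The conclusions within each cohort are not affected.

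**What to change.** If the pooled ANCOVA is kept, replace the line in SAP 13.0 with a full model statement:

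- Fixed factors: treatment (placebo, 60 mg, 120 mg) and cohort (1, 2).
- Covariate: continuous baseline ppFEV1.
- Say explicitly whether hypertonic saline use is also included, and delete the stray word. SAP 8.0 defines saline use for both cohorts, so either choice can be carried out.
- State that the model assumes the same 120 mg effect in both cohorts, and show the pooled 60 mg estimate next to the Cohort 1 estimate that is already planned.

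The cost is one degree of freedom (one more if saline use is added) and the small rise in standard error calculated above. No new data are needed. If d is below about 1.8 points, the term gives up a little precision for 60 mg in exchange for removing the bias.

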## 14.0 Validation

PRA's goal is to ensure that each TFL delivery is submitted to the highest level of quality. Our quality control procedures will be documented separately in the study specific quality control plan.

## Appendix 1 Glossary of Abbreviations

Glossary of Abbreviations:

Sponsor: SPYRYX Biosciences

Protocol no: SPX-101-CF-201

|                  |  |
|------------------|--|
| ADaM             | Analysis Data Model                          |
| AE               | Adverse event                                |
| AESI             | Adverse event of special interest            |
| AR1              | First order autoregressive                   |
| ALT              | Alanine aminotransferase test                |
| ALP              | Alkaline phosphatase test                    |
| ANOVA            | Analysis of variance                         |
| ANCOVA           | Analysis of covariance                       |
| AST              | Aspartate aminotransferase test              |
| BID              | Twice daily                                  |
| BMI              | Body mass index                              |
| CF               | Cystic Fibrosis                              |
| CFB              | Change from baseline                         |
| CFQ-R            | Cystic fibrosis questionnaire revised        |
| CRF              | Case Report Form                             |
| CS               | Compound symmetry                            |
| CSR              | Clinical Study Report                        |
| CTMS             | Clinical trials management system            |
| DSMB             | Data Safety Monitoring Board                 |
| ECG              | Electrocardiogram                            |
| ET               | Early termination                            |
| FEF              | Forced Expiratory Flow                       |
| FEV 1 | Forced expiratory volume in 1 second         |
| FVC              | Forced vital capacity                        |
| FU               | Follow up                                    |
| HE               | Health Economics                             |
| IP               | Investigational product                      |
| IPD              | Important protocol deviations                |
| ITT              | Intention-to-treat                           |
| IVRS             | Interactive Voice Response System            |
| MedDRA           | Medical Dictionary for Regulatory Activities |
| MMRM             | Mixed effect model repeated measures         |
| PDV              | Protocol deviation                           |
| PK               | Pharmacokinetic                              |

|                    |  |
|--------------------|--|
| PP                 | Per Protocol   |
| ppFEV 1 | Percent Predicted forced expiratory volume in 1 second |
| ppFVC              | Percent Predicted forced vital capacity                |
| QD                 | Once daily   |
| QoL                | Quality of Life  |
| SAP                | Statistical Analysis Plan                              |
| SAE                | Serious Adverse Event                                  |
| SAS                | Statistical analysis system                            |
| SDTM               | Standard Data Tabulation Model                         |
| TC                 | Telephone call   |
| TEAE               | Treatment-emergent adverse event                       |
| TFL                | Table, figures and listings                            |
| WHO                | World Health Organization                              |

## Appendix 2 Tables, Figures, Listings, and Supportive SAS Output Appendices

The TFL shells and table of contents are provided in a separate document titled “SPYPX101 TFL Shells Version 2\_0”.
